# 7.3. Participant Discontinuation/Withdrawal from the Study

- All efforts should be made to ensure participants are willing to comply with study participation prior to conducting the screening procedures.
- The study staff should notify Alexion and their site monitor of all study withdrawals as soon as possible. The reason for participant discontinuation must be recorded in the source documents and eCRF.
- A participant may withdraw from the study at any time at their own request or may be withdrawn at any time at the discretion of the Investigator for safety, behavioral, compliance, or administrative reasons. This activity is expected to be uncommon.
- At the time of discontinuing from the study, an early discontinuation visit should be conducted that includes the EOS assessments shown in the SoA, if possible (Section 1.3).
- All efforts will be made to contact participants who withdraw/are withdrawn from the study via phone for a safety follow-up call approximately 30 days (4.5 half-lives) after their dose to assess AEs.

- The first participant in each cohort to withdraw/be withdrawn from the study prior to completion of the EOS assessments may not be replaced; subsequent participants in that cohort to withdraw/be withdrawn before EOS completion will be replaced.
- If the participant withdraws consent for disclosure of future information, Alexion may retain and continue to use any data collected before such a withdrawal of consent.
- If a participant withdraws from the study, the participant may request destruction of any samples taken and not tested, and the Investigator must document this in the site study records.

## 7.4. Lost to Follow-up

A participant will be considered lost to follow-up if the participant repeatedly fails to return for scheduled visits and is unable to be contacted by the study site.

The following actions must be taken if a participant fails to return to the clinic for a required study visit:

- The site must attempt to contact the participant to reschedule the missed visit as soon as possible, counsel the participant on the importance of maintaining the assigned visit schedule, and ascertain whether or not the participant wishes to and/or should continue in the study.
- Before a participant is deemed lost to follow-up, the Investigator or designee must make every effort to regain contact with the participant (where possible, 3 telephone calls and, if necessary, a certified letter to the participant's last known mailing address or local equivalent methods). These contact attempts should be documented in the participant's medical record.
- Should the participant continue to be unreachable, they will be considered lost to follow-up.

Discontinuation of specific sites or of the study as a whole are handled as part of Section 10.1.8.

#### 8. STUDY ASSESSMENTS AND PROCEDURES

- Study procedures and their timing are summarized in the SoA (Section 1.3). Protocol waivers or exemptions are not allowed.
- Immediate safety concerns should be discussed with Alexion immediately upon occurrence or awareness to determine if the participant should continue or discontinue study intervention.
- Adherence to the study design requirements, including those specified in the SoA (Section 1.3), is essential and required for study conduct.
- All screening evaluations must be completed and reviewed to confirm that potential participants meet all eligibility criteria. The Investigator will maintain a screening log to record details of all participants screened and to confirm eligibility or record reasons for screening failure, as applicable.
- Procedures conducted as part of the participant's routine clinical management (eg, blood count) and obtained before signing of the ICF may be utilized for screening or baseline purposes provided the procedures met the protocol-specified criteria and were performed within the time frame defined in the SoA (Section 1.3).
- See Section 10.2 for the list of clinical laboratory tests.

## 8.1. Efficacy Assessments

No efficacy assessments will be performed during the study.

## 8.2. Safety Assessments

Planned time points for all safety assessments are provided in the SoA (Section 1.3).

#### 8.2.1. Physical Examinations

- Complete or brief physical examinations will be performed according to the timepoints indicated in the SoA (Section 1.3). Investigators should pay special attention to clinical signs related to previous serious illnesses.
- Complete physical examinations will include, at a minimum, assessments of the cardiovascular, respiratory, gastrointestinal, and neurological systems.
- Brief physical examinations will include assessments at the Investigator's discretion.
- Height and BMI will be recorded only at Screening.
- Weight will be recorded at Screening and Day -1.

## 8.2.2. Vital Signs

- Oral temperature, pulse rate, respiratory rate, and systolic and diastolic blood pressure (mm Hg) will be assessed.
- Blood pressure and pulse measurements will be assessed using a completely automated device after the participant has been resting in the supine position for at

least 5 minutes. At Screening, supine and standing (orthostatic) blood pressures will be performed according to the CRU's typical procedure to exclude participants who are prone to orthostatic hypotension. Manual techniques will be used only if an automated device is not available.

- Blood pressure and pulse measurements should be preceded by at least 5 minutes of rest for the participant in a quiet setting without distractions (eg, television, cell phones). Ideally, the same arm for each participant should be used for measurements.
- Vital signs taken postdose will be performed before the coinciding blood collection, whenever possible.

## 8.2.3. Electrocardiograms

- At each timepoint indicated in the SoA (Section 1.3), 12-lead ECGs will be performed in triplicate sequentially within 5 minutes, at least 1 minute apart to obtain heart rate, PR, QRS, QT, and QTc intervals.
- ECGs should not be performed within 1 hour after any major meal or major meals should be withheld until after ECG assessments.
- Participants should rest in supine position for at least 10 minutes before each ECG timepoint.
- Predose ECGs (Baseline) should be performed at least 1 minute apart after 10 minutes of bedrest in supine position (note, no bedrest is required post ECG), at 90, 75, and 60 minutes before dosing.
- Postdose ECGs will be performed before the coinciding blood collection, whenever possible.

#### 8.2.4. Clinical Safety Laboratory Assessments

- See Section 10.2 for the list of clinical laboratory tests to be performed and to the SoA (Section 1.3) for the timing and frequency.
- The Investigator must review the laboratory report, document this review, and record any clinically relevant changes occurring during the study in the AE section of the eCRF. The laboratory reports must be filed with the source documents.
- All laboratory tests with values considered clinically significantly abnormal during participation in the study should be repeated until the values return to normal or baseline or are no longer considered clinically significant by the Investigator or Medical Monitor.
  - If such values do not return to normal/baseline within a period of time judged reasonable by the Investigator, the etiology should be identified, and Alexion notified.
  - All protocol-required laboratory assessments, as defined in Section 10.2, must be collected in accordance with the Laboratory Manual and the SoA (Section 1.3).

- Laboratory assessments performed at the institution's local laboratory that require
  a change in participant management or are considered clinically significant by the
  Investigator (eg, AE or SAE) must be recorded in the eCRF.
- The maximum total blood volume collected from participants in this study will not exceed 500 mL. The National Health Service blood donation policy at the time of completion of this protocol (http://www.blood.co.uk/who-can-give-blood/) states that women can give 470 mL of blood every 16 weeks. Therefore, the ≤ 500 mL of blood collected during this study of less than 16 weeks is permitted/consistent with current clinical practice.

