# 4.5. Duration of Treatment and End of Study Definition

[figure not shown]
Following a Screening Period of up to 28 days, there will be a Dosing and Follow up Period (single dose on Day 1 through the EOS Visit) of approximately 74 days.

Based on data from preclinical models, the half-life of ALXN1910 is expected to be approximately 7 days in healthy adult participants; therefore, the end of study visit is planned on Day 75, representing approximately 10 half-lives after initial study intervention administration. The total study duration per participant is approximately 103 days. An overview of the study visits is present in Figure 2.

A participant is considered to have completed the study if they complete all visits of the study including the last scheduled visit specified in the SoA (Section 1.3).

The end of the study is defined as the date the last participant completes the last visit (as specified in the SoA [Section 1.3]).

Figure 2: Overview of Study Visits

Abbreviation: D = day

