#### Sex

2. Male or female, and willing to follow protocol-specified contraception guidance as specified in Section 10.7.

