### **Diagnostic Assessments**

- 15. Presence of fever (confirmed body temperature > 37.6°C) (eg, a fever associated with a symptomatic viral or bacterial infection) within 14 days prior to dosing on Day 1.
- 16. Alkaline phosphatase greater than the ULN or lower than the lower limit of normal of the reference range of the testing laboratory at Screening or on Day -1.
- 17. Serum creatinine greater than the ULN of the laboratory reference range at Screening or on Day -1; estimated glomerular filtration rate < 90 mL/min/1.73 m^2.
- 18. ALT or aspartate aminotransferase > ULN of the reference range of the testing laboratory at Screening or on Day -1.
- 19. Any clinically significant abnormal hematological parameters (per the Investigator's discretion).
- 20. Positive urine drug toxicology screen at Screening or on Day -1.
- 21. Positive urine alcohol test at Screening or Day -1
- 22. Donation of plasma within 7 days prior to dosing; donation or loss of blood (excluding volume drawn at Screening) of more than 50 mL within 30 days of dosing on Day 1, or more than 499 mL of blood within 56 days of dosing on Day 1.

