#### 8.5. Pharmacokinetics

- Whole blood will be collected for measurement of serum concentrations of ALXN1910 as specified in the SoA (Section 1.3). Samples collected within ± 10% in minutes or 30 minutes of the scheduled time, whichever is less, will not be considered a protocol deviation. Additional samples may be collected at additional time points during the study if warranted and agreed upon between the Investigator and Alexion. The IV dose cohorts (1 and 3) will also have an end-of-infusion PK time point. The total blood volume will not exceed the volume limit for healthy participants (Section 8.2.4). To ensure appropriate monitoring, the timing of sampling may be altered during the course of the study based on newly available data (eg, to obtain data closer to the time of peak serum concentrations or to extend the study duration to capture sufficient PK elimination phase).
- Instructions for the collection and handling of biological samples will be provided by Alexion. The actual date and time (24-hour clock time) of each sample collection will be recorded.
- Samples will be used to evaluate the PK of ALXN1910. Samples collected for analyses of ALXN1910 serum concentration may also be used to evaluate safety or efficacy aspects related to concerns arising during or after the study.

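### The 500 mL blood-volume cap rests on a 470 mL allowance for women, which it exceeds by 30 mL

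*Protocol*

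**What the plan says.** Protocol Section 8.2.4 (Clinical Safety Laboratory Assessments) makes three linked statements.

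- The limit: "The maximum total blood volume collected from participants in this study will not exceed 500 mL". It applies to all participants, with no separate figure by sex.
- The support: a National Health Service blood donation policy, reported as saying that "women can give 470 mL of blood every 16 weeks".
- The inference: "Therefore, the ≤ 500 mL of blood collected during this study of less than 16 weeks is permitted/consistent with current clinical practice".

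Three other places in the protocol bear on this.

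- Women may enrol. Section 5.1 (Sex) reads "Male or female, and willing to follow protocol-specified contraception guidance".
- Section 4.5 gives the length of participation: "The total study duration per participant is approximately 103 days".
- Section 8.5 allows additional pharmacokinetic samples by agreement between the investigator and the sponsor, and names the Section 8.2.4 limit as the bound on total volume.

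The SAP is silent on blood volume.

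**The concern.** The sentence that justifies the cap contradicts it. A policy allowing women 470 mL per 16 weeks cannot show that 500 mL in less than 16 weeks is permitted for women. It would show this only if the study spanned more than one allowance interval, or if the cap for women were lower, and neither is the case.

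What is at stake is a participant-protection limit, not an estimate. The cap is the only bound on what the study itself may draw, and it matters most for unscheduled blood: extra pharmacokinetic and pharmacodynamic samples (Sections 8.5 and 8.6), repeats of clinically significant abnormal tests (Section 8.2.4), and additional samples after a suspected hypersensitivity reaction (Section 1.3, Tables 2 and 3). As written, such draws could bring a woman to 500 mL with the protocol fully respected, although the allowance cited in support stops at 470 mL.

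**Working it through.** **Inputs, all from the protocol**

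| Quantity | Value | Source |
|---|---|---|
| In-study cap | 500 mL, both sexes | Section 8.2.4 |
| Cited allowance, women | 470 mL per 16 weeks | Section 8.2.4 |
| Participation | about 103 days | Section 4.5 |
| First and last possible study day | Day -29 and Day 75 | Section 1.3, Tables 2 and 3 |

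**Step 1. Is the study really shorter than 16 weeks?** The allowance interval is 16 × 7 = 112 days. Participation is 103 / 7 = 14.7 weeks, and 112 − 103 = 9 days to spare. The schedule agrees with Section 4.5: with no Day 0, Day -29 to Day 75 covers 29 + 75 = 104 calendar days, or 103 days from first to last. The protocol's premise on duration is therefore correct.

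**Step 2. How many allowances fit?** Since 103 is less than 112, participation falls inside one interval. One allowance of 470 mL applies, not two.

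**Step 3. Compare the cap with the allowance.** Excess = 500 − 470 = 30 mL. Relative excess = 30 / 470 = 6.4%.

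**Step 4. Is there another basis for 500 mL?** Section 8.5 only refers back to Section 8.2.4. Exclusion criterion 22 in Section 5.2 also mentions volumes, barring loss of "more than 50 mL within 30 days of dosing on Day 1, or more than 499 mL of blood within 56 days" of dosing, but it governs blood lost before dosing and is not offered as support for the cap. Neither document gives a further justification or a lower limit for women.

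**What cannot be computed.** The documents state no tube or per-visit volumes, so the planned total cannot be added up and set against either 470 mL or 500 mL. Prorating the allowance to 103 days is not appropriate either: the policy as printed gives a volume and a repeat interval, not a daily rate.

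**The case against.** The strongest reply is that the two quantities differ in kind. A donation takes its volume at one sitting, whereas the study's 500 mL is a ceiling on many small draws spread from Screening to Day 75. On that view the donation figure is a rough benchmark, and a spread-out total within about 6% of it can fairly be called consistent with practice. The ceiling may also never be approached, 30 mL is small, and criterion 22 shows the protocol using a threshold close to 500 mL over a shorter window.

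Much of this is right as to weight. No overdraw and no harm has been shown, and the excess is modest. It does not rescue the inference, for three reasons.

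- The protocol does not argue from the difference between serial sampling and donation. It cites the allowance and concludes that the volume is permitted as well as consistent with practice. A total above an allowance is not permitted by that allowance.
- A ceiling governs discretionary draws, and that is how Section 8.5 uses this one.
- Criterion 22 is an eligibility rule about prior loss. It does not protect the interval either. A woman who gave 470 mL 31 days before Day 1 breaches neither part of the criterion, yet Day 75 falls 31 + 74 = 105 days after that donation, still inside 112 days.

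One part of the reply does limit the remedy. The printed policy figure concerns women only, so the documents do not require a 470 mL cap for men.

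**Conclusion.** The concern holds. The operative blood-volume limit for female participants is 30 mL, or 6.4%, above the only allowance given in its support, and the study length leaves room for just one such allowance. The point is minor. It affects no endpoint, analysis set or estimate, and it does not show that the planned sampling is excessive.

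The conclusion rests on the two figures printed in Section 8.2.4 and the duration in Section 4.5. The donation policy itself was not consulted, so whether 470 mL is its correct or complete content is taken from the protocol. The actual sample volumes are unknown. If the scheduled total is well below 470 mL, the mismatch bears only on the room left for unscheduled samples.

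**What to change.** In Section 8.2.4, set the maximum at no more than 470 mL for women over their participation. The limit that Section 8.5 refers to would then agree with the policy cited. A single 470 mL cap for all participants would be simpler to operate, but that is a choice of convenience. If 500 mL is retained for men, the section should say what supports it, because the cited figure does not cover them.

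If the sponsor wishes to keep 500 mL for women, the 470 mL sentence must be replaced by a justification that does support 500 mL. Softening the wording around the present figure would leave the mismatch in place.

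The cost is one protocol sentence and up to 30 mL less room for unscheduled samples per woman. Before making the change, the sponsor should add up the scheduled volumes from the Laboratory Manual to confirm that they fit under 470 mL with some reserve.

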#### 8.2.5. Pregnancy

Pregnancy data from female participants and female spouses/partners of male participants will be collected from the time points specified in the SoA (Section 1.3). Any female participant who becomes pregnant during the study will be withdrawn from the study. If a pregnancy is reported, the Investigator must immediately inform Alexion within 24 hours of awareness of the pregnancy and follow the procedures outlined in Section 10.7.3.

## 8.3. Adverse Events and Serious Adverse Events Considerations

- The definitions of AEs and SAEs and specific reporting requirements can be found in Section 10.3.
- All AEs will be reported to the Investigator or qualified designee by the participant (or, when appropriate, by a caregiver, surrogate, or the participant's legally authorized representative).
- The Investigator and any qualified designees are responsible for detecting, documenting, and recording events that meet the definition of an AE or SAE and remain responsible for following up AEs that are serious, considered related to the study intervention or study procedures, or that caused the participant to discontinue the study intervention (see Section 7).
- Procedures for recording, evaluating, follow-up, and reporting AEs and SAEs are outlined in Section 10.3.

## 8.3.1. Time Period and Frequency for Collecting AE and SAE Information

- All AEs and SAEs will be collected from the signing of the ICF until the EOS visit on Day 75 as specified in the SoA (Section 1.3).
- All SAEs will be recorded and reported to Alexion immediately and under no circumstance should this exceed 24 hours of the Investigator's awareness, as indicated in Section 10.3. The Investigator will submit any updated SAE data to Alexion within 24 hours of the date the investigational site became aware of the event.
- Investigators are not obligated to actively seek AE or SAE data after conclusion of the study participation. However, if the Investigator learns of any SAE, including a death, at any time after a participant has been discharged from the study, and they

consider the event to be reasonably related to the study intervention or study participation, the Investigator must promptly notify Alexion.

### 8.3.2. Method of Detecting AEs and SAEs

- The method of recording, evaluating, and assessing causality of AE and SAE and the procedures for completing and transmitting SAE reports are provided in Section 10.3.
- Care will be taken not to introduce bias when detecting AEs and/or SAEs. Openended and non-leading verbal questioning of the participant is the preferred method to inquire about AE occurrences.

## 8.3.3. Follow-up of AEs and SAEs

After the initial AE/SAE report, the Investigator is required to proactively follow-up on each participant at subsequent visits/contacts. All SAEs will be followed up until resolution, stabilization, the event is otherwise explained, or the participant is lost to follow-up (as defined in Section 7.4). Further information on follow-up procedures is provided in Section 10.3.

## 8.3.4. Regulatory Reporting Requirements for SAEs

- Prompt notification of an SAE by the Investigator to Alexion is essential so that legal obligations and ethical responsibilities towards the safety of participants and the safety of a study intervention under clinical investigation are met.
- Alexion has a legal responsibility to notify both the local regulatory authority and other regulatory agencies about the safety of a study intervention under clinical investigation. Alexion will comply with country-specific regulatory requirements relating to safety reporting to the regulatory authority, IRBs/IECs, and Investigators.
- Alexion is required to submit individual suspected unexpected serious adverse reaction (SUSAR) reports (defined in Section 10.3.2) in the format of CIOMS I Form to health authorities and Investigators as required. Forms submitted to Investigators will be blinded to treatment assignment. In limited circumstances, the blind may be broken in the case of urgent safety issues that could compromise participant safety.
- An Investigator who receives an Investigator safety report describing an SAE or other specific safety information (eg, summary or listing of SAEs) from Alexion will review and then file it along with the IB and will notify the IRB/IEC, if appropriate according to local requirements.

## 8.3.5. Special Warnings and Precautions for Use

Please refer to the current ALXN1910 Investigator's Brochure for special warnings and precautions for use.

#### **8.4.** Treatment of Overdose

• For this study, any blinded dose of study intervention greater than that specified in the protocol will be considered a suspected overdose.

- Alexion does not recommend specific treatment for a suspected overdose and no antidote is currently available for ALXN1910.
- Overdoses are medication errors that are not considered AEs unless there is an untoward medical occurrence resulting from the overdose.
- In the event of a suspected overdose, the Investigator/Treating Physician should:
  - Contact the Medical Monitor immediately.
  - Closely monitor the participant for any AE/SAE.
  - Obtain a serum sample for PK analysis if requested by the Medical Monitor (determined on a case-by-case basis).
  - Document the quantity of the excess dose as well as the duration of the overdose in the eCRF.
- Decisions regarding dose interruptions or modifications will be made by the Investigator in consultation with the Medical Monitor based on the clinical evaluation of the participant.

